#### **4.4. Criteria for Subject Withdrawal**

##### **4.4.1. Withdrawal from Treatment**

The subject must be withdrawn in the event of any of the following:

- Occurrence of an event that would have been considered an exclusion criterion prior to enrollment, that is clinically relevant and affects the subject's safety, and if discontinuation is considered necessary by the investigator and/or Sponsor.
- Radiological disease progression, defined by RECIST 1.1 as defined in [Section 6.4.4.3](#), unless the subject is considered to derive clinical benefit from the treatment by the investigator, is clinically stable and there is agreement with the Sponsor ([Section 5.4.5](#)).

Clinical stability is defined by:

- Absence of new symptoms and signs indicating clinically significant disease progression
- No decline in ECOG performance status.
- Absence of rapid progression of disease or progressive tumor at critical anatomical sites (e.g., cord compression) requiring urgent alternative medical intervention.

- Note: For Phase 2, tumor assessments should be performed every 6 weeks ( $\pm$  3 days) from first treatment dose until discontinuation of treatment, regardless of reason for discontinuation. This includes patients who are being treated past disease progression. Clinical disease progression, in the absence of radiologic progression on the basis of RECIST 1.1, including 1 or more of the following:
  - signs and/or symptoms of consistent with clinically significant progression of disease, including worsening of laboratory values, appearance of new lesion/worsening of the lesion best seen clinically, etc.
  - decline in ECOG performance status
  - tumor progression at critical anatomical sites that requires urgent medical intervention (e.g., CNS metastasis with potential for cord progression)
  - initiation of chronic opiates, or initiation of chemotherapy or new antineoplastic therapy, palliative radiation therapy, or surgery
- Any Grade 2 drug-related uveitis or eye pain or blurred vision that does not respond to topical therapy and does not improve to Grade 1 severity within 2 weeks OR requires systemic treatment;
- Any Grade  $\geq$  2 drug-related pneumonitis or interstitial lung disease that does not resolve to dose delay and systemic corticosteroids (also see Pulmonary Immune Related Adverse Event Management Algorithm [[Section 5.6.3](#)]);
- Any Grade 2 or 3 drug-related toxicity that does not resolve in  $\leq$  6 weeks;

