- Any Grade 3 drug-related bronchospasm, hypersensitivity reaction, or infusion-related reaction, regardless of duration; with the exception of Grade 3 infusion-related reactions resolving within 6 hours and controlled with medical management;
- Any Grade 3 non-skin, drug-related AE lasting  $>$  7 days, with the following exceptions for uveitis, pneumonitis, bronchospasm, diarrhea, colitis, neurologic toxicity, hypersensitivity reactions, infusion reactions, endocrinopathies, and laboratory abnormalities:
  - Grade 3 drug-related uveitis, pneumonitis, bronchospasm, diarrhea, colitis, neurologic toxicity, hypersensitivity reaction, or infusion reaction of any duration requires discontinuation;
  - Grade 3 drug-related endocrinopathies adequately controlled with only physiologic hormone replacement do not require discontinuation;
  - Grade 3 drug-related laboratory abnormalities do not require treatment discontinuation except:
    - Grade 3 drug-related thrombocytopenia  $>$  7 days or associated with bleeding requires discontinuation;
    - Any drug-related liver function test (LFT) abnormality that meets the following criteria require discontinuation (also see hepatic immune-related AE management algorithm [[Table 7](#)]):

- ▶ AST or ALT  $> 8 \times$  ULN;
- ▶ Total bilirubin  $> 5 \times$  ULN;
- ▶ Concurrent AST or ALT  $> 3 \times$  ULN AND total bilirubin  $> 2 \times$  ULN;
- Any Grade 4 drug-related AE or laboratory abnormality, except for the following events, which do not require discontinuation:
  - Grade 4 neutropenia  $< 7$  days;
  - Grade 4 lymphopenia or leukopenia;
  - Isolated Grade 4 electrolyte imbalances/abnormalities that are not associated with clinical sequelae and are corrected with supplementation/appropriate management within 72 hours after their onset;
- Any AE, laboratory abnormality, or intercurrent illness which, in the judgment of the Investigator, presents a substantial clinical risk to the subject with continued treatment;
- Tumor flare phenomenon, defined as local pain, irritation, or rash localized at sites of known or suspected tumor does not require treatment discontinuation.
- Any requirement for  $\geq 10$  mg per day of prednisone (or equivalent) for  $> 6$  weeks;
- Any recurrence of a Grade 3 or 4 drug-related toxicity;
- Dose delay which results in no AGEN2034 dosing for more than 6 weeks.

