### 5.4.3. Treatment of Infusion Related Reactions

Acute infusion reactions (which can include cytokine release syndrome, angioedema, or anaphylaxis) are different from allergic/hypersensitive reactions, although some of the manifestations are common to both AEs. Signs and symptoms usually develop during or shortly

after drug infusion and generally resolve completely within 24 hours of completion of infusion. Signs/symptoms may include: allergic reaction/hypersensitivity (including drug fever); arthralgia (joint pain); bronchospasm; cough; dizziness; dyspnea (shortness of breath); fatigue (asthenia, lethargy, malaise); headache; hypertension; hypotension; myalgia (muscle pain); nausea; pruritus/itching; rash/desquamation; rigors/chills; sweating (diaphoresis); tachycardia; tumor pain (onset or exacerbation of tumor pain due to treatment); urticaria (hives, welts, wheals); vomiting.

For an individual subjects, once the AGEN2034 infusion rate has been decreased by 50% or interrupted due to an infusion-related reaction, it must remain decreased for all subsequent infusions to that subject. If the subject has a second infusion-related reaction that is Grade  $\geq 2$  on the slower infusion rate, infusion should be stopped and the subject should discontinue treatment. If a subject experiences a Grade 3 or Grade 4 infusion-related reaction at any time, the subject must discontinue treatment. If an infusion reaction occurs, all details about drug preparation and infusion must be recorded.

Should infusion reaction be considered a significant safety issue by the SMC, the SMC might decide to recommend premedication with an antihistamine and acetaminophen approximately 30 to 60 minutes before each dose of AGEN2034 (e.g., 25–50 mg diphenhydramine, 500–650 mg paracetamol IV or oral equivalent acetaminophen). This regimen may be modified based on local treatment standards and guidelines, as appropriate.

[Table 3](#) shows treatment guidelines for subjects who experience an infusion reaction associated with administration of AGEN2034.

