Grades 3 or 4  Grade 3: Prolonged (i.e., not rapidly responsive to symptomatic medication and/or brief interruption of infusion); recurrence of symptoms following initial improvement; hospitalization indicated for other clinical sequelae (e.g., renal impairment, pulmonary infiltrates).  Grade 4: Life-threatening; pressor or ventilatory support indicated.	
Stop infusion.
 
Additional appropriate medical therapy may include but is not limited to:
 
 
• IV fluids
 
• Antihistamines
 
• NSAIDS
 
• Acetaminophen
 
• Narcotics
 
• Oxygen
 
• Pressors
 
• Corticosteroids
 
• Epinephrine
 
 
Increase monitoring of vital signs as medically indicated until the subject is deemed medically stable in the opinion of the investigator.
 
Hospitalization may be indicated.
 
Subject is permanently discontinued from further study drug administration.
	No subsequent dosing.

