#### 5.4.4.2.2. *Criteria to Resume Treatment*

Subjects may resume treatment with AGEN2034 when drug-related AE(s) resolve(s) to Grade 1 or baseline value, with the following exceptions:

- Subjects may resume treatment in the presence of Grade 2 fatigue.
- Subjects who have not experienced a Grade 3 drug-related skin AE may resume treatment in the presence of Grade 2 skin toxicity.

- Subjects with baseline Grade 1 AST/ALT or total bilirubin who require dose delays for reasons other than a 2-Grade shift in AST/ALT or total bilirubin may resume treatment in the presence of Grade 2 AST/ALT or total bilirubin.
  - Subjects with combined Grade 2 AST/ALT AND total bilirubin values meeting discontinuation parameters ([Section 4.4.1](#)) should have treatment permanently discontinued.
- Drug-related pulmonary toxicity, diarrhea, or colitis must have resolved to baseline before treatment is resumed.
- Drug-related endocrinopathies adequately controlled with only physiologic hormone replacement may resume treatment.
- Subjects who received systemic corticosteroids for management of any drug-related toxicity must be off corticosteroids or have tapered down to an equivalent dose of prednisone  $\leq$  10 mg/day.

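### Protocol 4.4.1 exempts a Grade 3 infusion reaction that settles within 6 hours from mandatory withdrawal, while its next bullet, Section 5.4.3 and Table 3 all require stopping.

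*Protocol*

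**What the plan says.** Section 4.4.1 opens its list with "The subject must be withdrawn in the event of any of the following". One bullet names Grade 3 drug-related bronchospasm, hypersensitivity and infusion-related reactions whatever their duration, and then adds "with the exception of Grade 3 infusion-related reactions resolving within 6 hours and controlled with medical management".

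The bullet directly after it deals with Grade 3 non-skin drug-related events lasting more than 7 days. Its first sub-bullet lists events for which duration is irrelevant, ending with "hypersensitivity reaction, or infusion reaction of any duration requires discontinuation".

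Section 5.4.3 says "If a subject experiences a Grade 3 or Grade 4 infusion-related reaction at any time, the subject must discontinue treatment". The same sentence is printed a second time later in that section.

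Table 3, in the row for Grades 3 or 4, says "Subject is permanently discontinued from further study drug administration". In the column for premedication at the following dose it says only "No subsequent dosing". The table's description of Grade 3 begins "Prolonged (i.e., not rapidly responsive to symptomatic medication and/or brief interruption of infusion" and goes on to symptoms that recur after initial improvement and to sequelae for which hospitalization is indicated.

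The 6-hour wording also appears in Section 3.1.1, as an exception to the definition of a dose-limiting toxicity.

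**The concern.** For one event, a drug-related Grade 3 infusion reaction that settles within 6 hours under treatment, the protocol gives opposite instructions. The exemption is explicit, and no sentence says that it is overridden. A site looking for permission to continue would find it in the withdrawal section, which is where an investigator would look first.

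What is at stake is re-exposure after a severe infusion reaction, in a trial planned for about 60 Phase 2 centers (Section 11.2) that may not all read the text alike. A site that used the exemption would also have no premedication instruction for the next dose, because Table 3 does not expect one to be given.

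**Working it through.** The point is textual, so there is no figure to reproduce. The check takes one event through each rule that could apply: a drug-related Grade 3 infusion reaction, controlled medically and resolved within 6 hours.

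| Place in the protocol | Instruction for this event | 6-hour exception? |
|---|---|---|
| 4.4.1, bullet on bronchospasm, hypersensitivity and infusion reactions | Withdrawal not mandatory under this bullet | Yes |
| 4.4.1, next bullet, first sub-bullet | Discontinue, any duration | No |
| 5.4.3, printed twice | Discontinue, at any time | No |
| Table 3, Grades 3 or 4 row | Discontinue permanently, no further dose | No |

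Count: 1 exempting clause against 3 separate stopping rules. Places where stopping is printed: 1 (4.4.1 sub-bullet) + 2 (5.4.3) + 1 (Table 3) = 4. Only Table 3 says the discontinuation is permanent.

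Four readings might reconcile the text.

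1. *The lead-in to 4.4.1.* Withdrawal is triggered by any one item on the list, so an exception inside one bullet does not cancel another bullet. On a strict reading the subject is withdrawn. That reading leaves the exemption with no effect at all, and the protocol does not say that this is intended.
2. *The definition of Grade 3.* Table 3 describes the reaction as prolonged but sets no limit in hours. Sections 3.1.1 and 4.4.1 both recognise Grade 3 reactions that resolve within 6 hours. The event is narrow, but it is not ruled out.
3. *The exception in 3.1.1.* There the wording decides only what counts as a dose-limiting toxicity. A dose-limiting toxicity does force permanent withdrawal, so in dose escalation the exception removes that one route to withdrawal. It does not lift 5.4.3 or Table 3.
4. *The criteria for resuming treatment.* Section 5.4.4.2.2 says "Subjects may resume treatment with AGEN2034 when drug-related AE(s) resolve(s) to Grade 1 or baseline value", followed by a list of exceptions. The number of those exceptions that name infusion reactions is 0, so the section does not block re-dosing.

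The surrounding text points towards stopping. Section 5.4.3 allows further dosing after mild or moderate reactions. Table 3 permanently stops a subject who has Grade 2 toxicity despite adequate premedication. The 4.4.1 exemption would therefore treat some Grade 3 reactions more leniently than that Grade 2 case.

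**The case against.** The strongest reply is that all the rules can be obeyed together by stopping. To re-dose, a site would have to disregard the adjacent bullet, 5.4.3, and both columns of Table 3. Section 5.4.3 also tells sites to manage any infusion toxicity according to Table 3, which shows which text is meant to govern. On this view the exempting clause is redundant wording, and removing it is a minor editorial matter. The resume criteria add little, because they concern delayed dosing and this subject would already be off treatment.

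Much of this is right. Stopping does satisfy every statement, and the direction to Table 3 is a real guide. But that direction does not mention 4.4.1 or its exception, so it is not an express override. It is a further reason to delete the clause. The remark about the resume criteria is also fair: they do not create the problem, they only fail to correct it.

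The safeguards are real too:

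- Every infusion reaction is an event of special interest, reportable to the sponsor within 24 hours (7.1.8), so the sponsor can correct a site before the next 2-weekly dose.
- The Safety Monitoring Committee reviews Phase 2 safety on an ongoing basis (3.2).
- Section 4.4.1 withdraws a subject on any recurrence of a Grade 3 or 4 drug-related toxicity, and where the investigator judges continued treatment a substantial clinical risk.
- Section 5.4.3 stops treatment after a second reaction of Grade 2 or higher at the slower infusion rate.
- An event that leads to inpatient hospitalization is a serious adverse event (7.1.4).

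These make harm less likely and limit its repetition. They do not settle which rule applies, and the two recurrence rules act only after the subject has been re-exposed.

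**Conclusion.** The inconsistency is real and lies in current operative text. It should be fixed because it concerns a patient-safety stopping rule, but its reach is small. It applies only to a reaction that is Grade 3 by Table 3 and still resolves within 6 hours. It can matter only for a subject's first such reaction, since 4.4.1 withdraws on recurrence. The documents give no frequency, so the number of subjects affected cannot be estimated.

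That a site might re-dose is an inference from the wording; nothing in the documents shows that it has happened. Whether the clause was carried over from the 3.1.1 definition is likewise only a guess. No effect on the objective response rate, the sample size or the power is claimed.

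**What to change.** Delete the exempting clause from the 4.4.1 bullet so that the bullet ends where it says that duration does not matter. Leave the 3.1.1 exception as it is, because it serves the definition of a dose-limiting toxicity.

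If the sponsor does intend the exemption, write it in identical terms into the next 4.4.1 sub-bullet, both statements in 5.4.3, and the Grades 3 or 4 row of Table 3. The next-dose column of that row would then also need a premedication instruction.

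The preferred change removes 17 words in the next amendment and needs a short letter to sites. It adds no visits, procedures or data.

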#### 4.4.2. Withdrawal from the Trial

Subjects are free to discontinue the trial at any time without giving their reasons. A subject must be withdrawn in the event of any of the following:

- Withdrawal of the subject's consent.
- Participation in any other therapeutic trial during the treatment duration of this trial.

If a subject has failed to attend scheduled trial assessments, the investigator must determine the reasons and the circumstances as completely and accurately as possible.

In case of premature withdrawal from the trial, the investigations scheduled for the Discontinuation Visit should be performed (Section 6.1) if possible, with focus on the most relevant assessments. In any case, the appropriate electronic case report form (eCRF) section must be completed.

#### **4.4.3. Premature Discontinuation of the Trial**

The entire trial may be discontinued prematurely in the event of any of the following:

- New information leading to unfavorable risk-benefit judgement of AGEN2034, e.g., due to:
  - Occurrence of significant previously unknown adverse reactions, or unexpectedly high intensity or incidence of known adverse reactions.
  - Other unfavorable safety findings.

Note: Evidence of inefficacy may arise from this trial or from other trials of AGEN2034, and unfavorable safety findings may arise from clinical or non-clinical examinations (e.g., toxicology).

- Sponsor's decision that continuation of the trial is unjustifiable for medical or ethical reasons.
- Poor enrollment of subjects, making completion of the trial within an acceptable timeframe unlikely.
- Discontinuation of development of AGEN2034.

Health authorities and Independent Ethics Committees (IECs)/Institutional Review Boards (IRBs) will be informed about trial discontinuation in accordance with applicable regulations.

The entire trial may be terminated or suspended upon request of health authorities.

## **5. STUDY DRUGS AND TREATMENT**

### **5.1. Investigational Medicinal Product**

The investigational medicinal product (IMP), also known as study drug, is AGEN2034, a novel, fully human monoclonal IgG4 antibody designed to block PD-1.

AGEN2034 drug product is supplied as a sterile, single-use solution for IV injection in a 2 mL or 10 mL glass vial. AGEN2034 should be stored in a refrigerator at 2°C to 8°C.

Each drug product 2 mL vial contains a withdrawable volume of 1 mL with 50 mg AGEN2034 at a nominal concentration of 50 mg/mL formulated in [REDACTED] [REDACTED]. Each drug product 10 mL vial contains a withdrawable volume of 5 mL with 50 mg AGEN2034 at a nominal concentration of 10 mg/mL formulated in [REDACTED] [REDACTED].

Please refer to the current version of the Investigator's Brochure and/or Pharmacy Manual for complete storage, handling, dispensing, and infusion information for AGEN2034.

## **5.2. Packaging and Labeling**

Study drug packaging and labeling will be in accordance with applicable local regulatory requirements and applicable Good Manufacturing Practice guidelines. The following information will be pre-printed on the vial: vial contents, storage conditions, and lot number. The label will also contain a statement to conform with FDA Investigational New Drug (IND) requirements as follows:

"Caution: New Drug - Limited by federal law to investigational use."

All study drug must be kept in a secure place under appropriate storage conditions. The sponsor or its representatives must be granted access on reasonable request to check drug storage, dispensing procedures, and accountability records. Refer to the Pharmacy Manual for additional details.

## **5.3. Storage and Dispensing**

The product storage manager should ensure that study drugs are stored in accordance with the environmental conditions (temperature, light, and humidity) as determined in the Pharmacy Manual. If concerns regarding the quality or appearance of the study drug arise, the study drug should not be dispensed and Sponsor should be contacted immediately.

Study drug documentation must be maintained including all processes required to ensure drug is accurately administered. This includes documentation of drug storage, administration and, as applicable, storage temperatures, reconstitution, and use of required processes (e.g., required diluents, administration sets).

AGEN2034 will be shipped in transport cool containers (2°C to 8°C) that are monitored with temperature control devices.

AGEN2034 drug product must be stored at 2°C to 8°C until use, with a temperature log maintained daily. All medication boxes supplied to each study center must be stored carefully, safely, and separately from other drugs.

For application in this trial, AGEN2034 drug product must be diluted with 0.9% saline solution (sodium chloride injection). Detailed information on infusion bags and medical devices to be used for preparation of dilutions and subsequent administration is provided in the Pharmacy Manual.

Once the vial is punctured, the AGEN2034 drug product must be diluted into appropriate volume of 0.9% saline solution in an infusion bag immediately. Infusion from the bag should begin within 24 hours of vial puncture when the bag is stored either at room temperature or at 5°C ± 3°C (refrigerated conditions).

Any unused portion of solution should be discarded in biohazard waste disposal, with final disposal by accepted local and national standards of incineration.

Please refer to the current version of the Investigator's Brochure and/or Pharmacy Manual for complete storage, handling, dispensing, and infusion information for AGEN2034.

## 5.4. Dosage and Administration

### 5.4.1. AGEN2034

AGEN2034 infusions should be administered within 60 minutes (-10/+20 min) using an infusion pump. A central catheter is not required for infusion; however, if a subject has a central venous catheter in place, it is recommended that it be used for the infusion. Once the infusion is completed, all remaining drug solution in the line should be administered according to institutional guidelines for saline flushing.

#### 5.4.1.1. Treatment Regimen

In Phase 1, the dose levels and schedules shown in Table 2 will be studied.

**Table 2: Phase 1 Dosing Regimens**

Part and Agent	Dose	Schedule	Duration of Treatment
Part A1: Dose Level 1			
AGEN2034	1 mg/kg IV 	Every 2 weeks	Up to 24 months
Part A1: Dose Level 2			
AGEN2034	3 mg/kg IV 	Every 2 weeks	Up to 24 months
Part A1: Dose Level 3			
AGEN2034	10 mg/kg IV 	Every 2 weeks	Up to 24 months
Part A2: Dose Level 1			
AGEN2034	6 mg/kg IV 	Every 3 weeks	Up to 24 months
Part A2: Dose Level 2			
AGEN2034	10 mg/kg IV 	Every 3 weeks	Up to 24 months

 Infusion time is 60 minutes (-10/+20 min)

In Phase 2, all subjects will receive AGEN2034 at a dose of 3 mg/kg IV over 60 minutes (-10/+20 min) every 2 weeks for up to 24 months.

In both Phases, subjects will be treated for up to 24 months, regardless of dose delays, as long as the subject meets criteria to remain on therapy.

### 5.4.2. Premedication

Premedication should not be administered routinely prior to dosing of drugs. See Section 5.4.3 for subsequent premedication recommendations following AGEN2034-related infusion reactions.

